PPC	Hi, this is [Staff First Name] from PPC. [Pt first name] is due for a check up. I'll call in a day or two to help schedule that appointment or you can walk in today to have your child seen! You can also call [contact], option 1 to schedule.	Hi, this is [First Name] from PPC. I noticed that [Child's First Name] is due for a check up. Can I schedule that for your right now? Alternate script for leaving a voice message: Hi, this is [First Name] from PPC. I noticed that [Child's First Name] is due for a check up. Sorry I missed you. Please call [contact], option 1 to schedule your appointment or walk in today to have your child seen.

*Scripts have been translated into Spanish versions by Interpreter Services

Response variables (outcomes):

- Appointment **was scheduled** within 2 weeks of intervention (Y/N) (date of actual appointment may be greater than 2 weeks from intervention)
- Appointment **was completed** within 8 weeks of intervention (Y/N). Appointment completed within 8 weeks of randomization will be used for group who does not receive any intervention.
- (Primary Outcome) Receipt of MMR by 15 months of age or receipt of 2nd MMR dose by 3 months after randomization (Y/N)
- Receipt of 1st COVID vaccination (ages 12-17 years) within 8 weeks of first intervention (Y/N)
- Family member receipt of COVID vaccination in our health system within 8 weeks of first intervention

Blocking: (controlling for factors that might influence the outcome)

- Age (12-14 months, 4 years)
- Clinic location (PPC, HPC, FPC)

Personal Contacts (12-14 months & 4-year-olds) Trial:

Randomization: Eligible patient will be identified by running a report in the electronic health record (EHR). We will run this report, stratified by clinic location, and randomly assign patients into one of the four groups created by our 2 X 2 design. Groups will receive their assigned intervention in one of four successive weeks with the sequence randomly assigned (see table below).

Replication: We will conduct a total of 3 trials, repeating the randomization procedure every 4 weeks to identify children who become eligible: Weeks 1-4 = trial #1, weeks 5-8 = trial #2, weeks 9-12 = trial #3.

Outreach Methods Study Protocol & SAP

Version 1.1, 1/14/22

	1 automated message sent	2 automated messages sent
0 personal contact attempt	Message sent on Thu (weeks 3, 5, 10)	Message sent on Thu & Fri (weeks 4, 6, 12)

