1 personal contact attempt	Above plus attempt Mon – Fri of following week (weeks 2, 7, 11)	Above plus attempt Mon – Fri of following week (weeks 1, 8, 9)

MyChart and Televox Trials (6-17 years old):

Randomization: Eligible patients will be identified by running a report in the electronic health record (EHR). We will run this report, stratified by clinic location, and randomly assign patients into one of the study groups as described above. Groups will receive their assigned intervention in one of four successive weeks with the sequence randomly assigned (see table below).

We will randomize children who are eligible and implement interventions for each trial : Weeks 1-3 = Televox Trial 12-17yo, Weeks 4-7 = Televox Trial 6-11yo, Weeks 8-10 = MyChart Trial.

MyChart Trial:

	no message	1 MyChart message sent	2 MyChart messages (e.g. Mon and Thurs)
Standard Message	No intervention	Week A	Week B
Tailored Message		Week A	Week B

Televox (6-11yo) Trial:

no message	Low Tailored Message 2 automated standard messages sent (e.g. Thu, Fri) (weeks C, C)	High Tailored Message 2 automated tailored messages sent (e.g. Thu, Fri) (weeks D, D)
-------------------	--	---

Televox (12-17yo) Trial:

no message	Low Tailored Message 2 automated tailored messages sent (e.g. Thu, Fri) (week A)	COVID Tailored Message 2 automated messages sent (e.g. Thu, Fri) (week B)
-------------------	--	---

Of note, automated messages and/or personal contact attempts will not be completed if the parent schedules an appointment after being randomized but before receiving the intervention.

Covariates for logistic regression: (factors that might influence the outcome if not balanced across groups)

1. Child age at the time of randomization (rationale: visits are less frequent for children age 4 years)
2. Parent preference for call vs. text mode of contact (rationale: calls may be more likely to get blocked than texts)
3. Parent with activated MyChart account (Y/N) (rationale: not dependent on calling scheduling center to make appointment)

4. Access to appointment: Number of days to 3rd next available appointment at patient's clinic at time their first automated message is sent
5. Patient receipt of any past immunizations (Y/N) (rationale: vaccine refusing parents will be unlikely to change even if they return for well child check)
6. School-age vs. adolescent patient age (rationale: adolescents less likely to get yearly check-ups)
7. Historical no-show rate

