For the Personal Contact (12-14 mo & 4 years old) trials, we will conduct intent-to-treat analyses using logistic regression models (without adjusting for covariates) for each of our three binary outcomes: completed appointment within 2 weeks, completed appointment within 8 weeks, receipt of MMR by 15 months of age or receipt of 2nd MMR by 3 months after randomization. We will do pair-wise comparison among the 4 groups and adjust p value of each comparison for multiplicity. If participants in the 4 groups differ on potential covariates, we will conduct additional analyses adjusted for these variables.

For the MyChart and Televox Trials (6-17 years old), we will conduct intent-to-treat analyses using logistic regression models (without adjusting for covariates) for each of the binary outcomes: scheduled appointment within 2 weeks, completed appointment within 8 weeks, receipt of 1st dose of COVID vaccination (age 12-17 years) within 8 weeks, family member receipt of COVID vaccination within 8 weeks. We will do pair-wise comparison among the treatment groups and adjust p value of each comparison for multiplicity. If participants differ in potential covariates across treatment groups, we will conduct additional analyses adjusted for these variables. We will explore non-inferiority analysis for comparison the two groups that are expected to have similar appointment scheduled and completion rate in the MyChart trial.

We will also conduct per-protocol analyses according to the interventions actually received by the participants, recognizing that actual intervention received could be different from initial randomized intervention. For example, a parent allocated to group A might schedule an appointment after receiving the automated message and therefore would not receive a personalized contact attempt. In addition, we may explore potential interaction between the two interventions as a secondary analysis. All analysis will be conducted using SAS version 9.4.

Duration

The study will begin upon IRB approval and continue through December 31, 2022. During this time, we will discuss the significance of data, potential future projects and dissemination of results.

Process of Obtaining Consent

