The results of the Outreach Methods study will be assessed as described in this document. This statistical analysis plan begins with an overview of the key components of the study, including its design, objectives, and outcomes measures. This is followed by a detailed description of the statistical analyses that will be utilized to address study hypotheses.

1. Overview of study: This study used a multi-arm randomized control trial to test the impact of automated text/telephone messages, with and without information about COVID-19 vaccine availability, on the scheduling and completion of adolescent well-care visits (AWC). We randomized eligible patients to the Standard Message group, the COVID-19 Vaccine Message group, or the Control Group. We generated random allocation sequence stratified by clinic location using block randomization (with a block size of 3). Based on sample size calculations, we planned to enroll a minimum of 859 subjects overall aged 12-17 years old that met eligibility criteria based on data obtained from the electronic health record (EHR) from three academic pediatric primary care practices.

1.1 Study Objective: Test the effectiveness of text and telephone messages, with and without information about COVID-19 vaccine availability, on the scheduling and completion of adolescent well-care visits (AWC) in adolescents due for preventative services.

Working hypothesis: Twenty percent of patients in the Standard Message group, 30% of patients in the COVID-19 vaccine group, and 2% of those in the control group will complete an adolescent well-care visit within 8 weeks.

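### Clinic stratifies allocation in every trial but appears in no stated main model, so a small amount of power and risk-difference precision is given up

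*Combined protocol and SAP*

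**What the plan says.** **Allocation.** For Personal Contacts the protocol states: "We will run this report, stratified by clinic location, and randomly assign patients into one of the four groups created". For the MyChart and Televox trials: "We will run this report, stratified by clinic location, and randomly assign patients into one of the study groups as described above". SAP section 1, which covers only the 12-17 trial, adds the block scheme: "We generated random allocation sequence stratified by clinic location using block randomization (with a block size of 3". The protocol's list headed "Blocking: (controlling for factors that might influence the outcome" includes "Clinic location (PPC, HPC, FPC".

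**Analysis.** The protocol's Analysis section plans "intent-to-treat analyses using logistic regression models (without adjusting for covariates" for both families of trials. Pairwise comparisons are to be adjusted for multiplicity by an unnamed method. SAP 2.3.2 and 2.3.3 describe logistic models comparing the three randomized groups and name no other term.

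**Adjustment.** The protocol describes its covariates as "factors that might influence the outcome if not balanced across groups". Adjustment is a second step: "If participants in the 4 groups differ on potential covariates, we will conduct additional analyses adjusted for these variables". SAP 2.3.2 and 2.3.3 say the same for their models. SAP 2.3.1 says, without that limit, that baseline characteristics showing large differences will enter the analyses. Clinic is absent from the protocol's eight covariates, from the descriptive list in its Analysis section, and from the baseline list in SAP 2.3.1.

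**The concern.** The plan treats clinic as a factor that may influence outcome and controls it at allocation, then does not carry it into any stated model. If clinics differ in how often visits are completed, that variation stays in the error term although the design has already balanced it across arms.

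The plan's own safety net does not help. Adjustment follows imbalance, and stratified blocking prevents imbalance on clinic. The value of a stratification factor in the model lies in how well it predicts outcome, which an imbalance rule does not look at.

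At stake is a little power for the message comparisons, and a little precision if risk differences are reported. A smaller matter is that SAP 2.3.1, read alone, leaves unclear whether imbalanced covariates enter the main model or only the additional ones.

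**Working it through.** **Reproducing the plan's figure.** With two-sided alpha 0.05, 80% power, pooled variance and no continuity correction, 20% vs 30% needs 293.2 per group, against 293 in the protocol. For 30% vs 40% the formula gives 355.9, against 356. The SAP minimum of 859 is 859/3 ≈ 286 per arm.

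**Balance in the 12-17 trial.** A block of 3 for three arms, with equal allocation, holds one patient per arm. Only an incomplete last block in a clinic can unbalance the arms, by at most 1 patient per clinic. No block scheme is stated for the other trials.

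**Inputs for the gain.** SAP working hypothesis, Standard 20% vs COVID message 30%, n = 286 per arm. Assumed, because the documents give no clinic rates: three equal clinics, balance within clinic, clinic log-odds offsets of −s, 0, +s, and arm averages held at 20% and 30%.

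- s = 0.5: clinic rates 13/19/28% (Standard) and 20/29/41% (COVID message); odds span e^1 = 2.7-fold.
- s = 1.0: 7/17/36% and 12/27/51%; odds span e^2 = 7.4-fold.

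**Variance.** Total: V = 0.20×0.80 + 0.30×0.70 = 0.37. Within clinic (average binomial variance over clinics, summed over the two arms):

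- s = 0.5: 0.1559 + 0.2030 = 0.3589; ratio 0.970, square root 0.985.
- s = 1.0: 0.1457 + 0.1851 = 0.3308; ratio 0.894, square root 0.946.

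**Risk-difference half-width**, 1.96×√(V/286): 7.05 points from the total variance; 6.94 (s = 0.5) or 6.67 (s = 1.0) from the within-clinic variance.

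**Power at nominal 5%.** SE_tot = √(0.37/286) = 0.0360; SE_w = 0.0354 or 0.0340. Without clinic, the test uses SE_tot while the estimate varies with SE_w, so power = Φ((0.10 − 1.96×SE_tot)/SE_w). With clinic, power = Φ(0.10/SE_w − 1.96).

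| s | without clinic | with clinic | gain (points) |
|---|---|---|---|
| 0 | 79.4% | 79.4% | 0 |
| 0.5 | 79.8% | 80.6% | 0.8 |
| 1.0 | 80.7% | 83.7% | 3.0 |

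Simulated logistic models gave 79.4 vs 80.4% and 80.3 vs 83.5%. If Bonferroni over three comparisons is assumed, the same formulas give 65.3 vs 66.6% and 65.9 vs 70.8%.

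**Type I error without clinic** (25% vs 25%), 2Φ(−1.96/√ratio): 5.0%, 4.7% and 3.8% at s = 0, 0.5 and 1.0.

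**Odds ratio.** Unadjusted: (0.30/0.70)/(0.20/0.80) = 1.71, with SE of the log √(1/(286×0.16) + 1/(286×0.21)) = 0.196. With clinic, the conditional odds ratio is 1.74 (SE 0.199) at s = 0.5 and 1.83 (SE 0.208) at s = 1.0. The ratio of log odds ratio to SE rises from 0.539/0.196 = 2.75 to 0.556/0.199 = 2.79 and 0.602/0.208 = 2.90. The test gains, but the log-odds-ratio interval gets slightly wider.

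**Other trials.** In simulation, the protocol's 12-17 figures (30% vs 40%, 356 per arm) gain 1.1 and 3.6 points. For Televox 6-11, MyChart and Personal Contacts the gain is 0.2-0.8 and 2.7-3.1 points if arms are balanced within clinic. If patients were assigned within clinic without blocks it is 1.1-1.5 and 4.0-5.4.

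**The case against.** The strongest reply is that this is an optional gain on top of a valid analysis, and that the larger gains need an implausible spread. Three practices of one institution would have to differ 7.4-fold in odds to reach 3 points; at a 2.7-fold span the gain is about 1. This stands, and it makes the point minor.

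Second, a reader might infer that intervals are wider than they need be. For the planned estimand, the odds ratio, that is not so: adding clinic raises its log-scale standard error. The precision claim holds only for a risk difference, which the plan does not currently report.

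Third, the 12-17 SAP is dated 1/14/22 and puts the study end at 8/5/21. Replacing the protocol's unadjusted model after that date for about a point of power is a real cost. It stands as a condition on the fix: the change must be disclosed and the unadjusted result shown with equal prominence.

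Fourth, the protocol keeps its Blocking list apart from its covariate list, so leaving out covariates need not mean leaving out clinic, and the SAP models name a comparison rather than every term. This is fair. What can be said is that no stated model includes clinic.

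Fifth, the protocol's covariate on days to the third-next-available appointment is measured at the patient's clinic. It is at most a partial proxy, enters only additional analyses, and is not on the SAP's baseline list.

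**Conclusion.** The point holds as a minor, inexpensive improvement. Clinic is used in allocation in every trial and appears in no stated main model, and in the 12-17 trial the imbalance rule would not bring it in. The cost is nil if clinics are alike, about 1 power point at ±0.5 log-odds, and about 3 points at ±1.0, which is taken as the upper end of the range. These sizes are for 20% vs 30% at 286 per arm and nominal 5%. They rest on an assumed clinic spread, three equal clinics and balance within clinic; balance is documented only for the 12-17 trial.

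A reader might infer that omitting a stratification factor biases the comparison, inflates type I error or leaves the trials underpowered. The documents do not support this. Randomization within clinic protects the comparison, the unadjusted error rate in the 12-17 setting is at or below 5%, and power without clinic does not fall below its level with no clinic effect.

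A reader might also take SAP 2.3.1 to contradict 2.3.2 and 2.3.3. The sentences can be read together, and the protocol's Analysis section makes the unadjusted model the main one, so this is only an editorial point.

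**What to change.** 1. Include clinic as a factor in the main logistic model of each trial. Keep the planned group comparisons and the multiplicity adjustment.
2. Beside the clinic-conditional odds ratios, report risk differences standardized over clinic, and show the protocol's unadjusted model alongside.
3. In the 12-17 trial, label clinic adjustment as introduced after 8/5/21 and give the unadjusted result equal prominence. Use the same label in any other trial whose outcomes had been seen.
4. In SAP 2.3.1, state that covariates triggered by imbalance enter additional analyses only, in line with 2.3.2, 2.3.3 and the protocol's Analysis section.
5. State for each trial whether assignment was blocked within clinic.

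**Cost.** Some SAP wording and two model terms. Clinic is already known from allocation, and the 286×(0.02 + 0.20 + 0.30) ≈ 149 events expected in the 12-17 trial comfortably support two arm and two clinic terms. The downside is that the odds ratio becomes conditional on clinic (about 1.71 moving to 1.74-1.83), which is why the standardized risk differences belong beside it.

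### As written, the Personal Contact analysis models a visit completed within 2 weeks, which the protocol never defines, and omits the defined outcome of an appointment scheduled within 2 weeks

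*Combined protocol and SAP*

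**What the plan says.** The protocol's list under Response variables (outcomes) gives one outcome with a two-week window: "Appointment was scheduled within 2 weeks of intervention (Y/N". A parenthesis separates booking from attendance: "date of actual appointment may be greater than 2 weeks from intervention". The list gives one completion outcome, with an eight-week window, and adds a rule for untreated children: "Appointment completed within 8 weeks of randomization will be used for group who does not receive any intervention". It marks MMR receipt as the primary outcome.

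The Analysis section then states what will be modelled in the Personal Contact trial. It announces logistic regression "for each of our three binary outcomes" and names them: "completed appointment within 2 weeks, completed appointment within 8 weeks", and then MMR receipt by the age of 15 months (or, for the older children, the second MMR dose). No scheduling outcome appears.

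The next paragraph of that section, on the MyChart and Televox trials, opens its own list differently: "scheduled appointment within 2 weeks, completed appointment within 8 weeks".

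**The concern.** The outcomes list and the analysis text describe different variables for the same two-week window, and the analysis text is what a programmer would follow. Three things make this more than a matter of style.

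- Scheduling is in the official title and the Objective. It is also what the personal contact directly seeks, since the medical assistant's call script offers to book on the spot.
- Two-week completion has no definition in the protocol. If both clocks start together, every visit completed within two weeks is also completed within eight. The written list would then hold two overlapping completion outcomes and no scheduling outcome. Overlap is not a defect in itself, but here it displaces a distinct outcome.
- With two candidate variables for one window, the choice between them could be made after the results are known.

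**Working it through.** The point turns on wording, so the check sets the texts side by side.

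| Place | Two-week outcome | Completion outcome |
|---|---|---|
| Protocol, Objective (includes 12-14 months and 4 years) | scheduling named, no window | completion named, no window |
| Protocol, Response variables | scheduled | 8 weeks only |
| Protocol, Analysis, Personal Contact | **completed** | 8 weeks |
| Protocol, Analysis, MyChart/Televox | scheduled | 8 weeks |
| SAP 1.2 and 2.3.3 (ages 12-17 only) | scheduled | 8 weeks |

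**Step 1: is two-week completion defined anywhere?** No. The only completion window in the outcomes list is eight weeks. The randomization-date rule attached to it does not create another, and every Personal Contact group receives at least one automated message in any case.

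**Step 2: does the count of outcomes help?** The Objective names three outcomes for these ages: scheduling, completion and MMR. The Personal Contact paragraph also counts three, but fills them with completion, completion and MMR. The total agrees and one item does not, which is the pattern expected if one word was mistyped.

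**Step 3: does other text supply the scheduling analysis?** No. SAP sections 1 and 1.1 confine that document to the adolescent trial. The protocol's Analysis section is the only analysis plan for the Personal Contact trial.

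**Step 4: does the choice of variable change a child's result?** Take a visit booked on day 5 and held on day 20.

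- Scheduled within 2 weeks: 5 ≤ 14, so yes.
- Completed within 2 weeks: 20 > 14, so no.
- Completed within 8 weeks: 20 ≤ 56, so yes.

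The child is a success under the outcomes list and a failure under the analysis text. The documents give no distribution of booking-to-visit times, so the share of children affected cannot be computed.

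**Step 5: is the sample size touched?** No. The Personal Contact table is labelled as MMR receipt. Its figures follow from the unpooled two-proportion formula with two-sided alpha 0.05 and 80% power:

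n = (1.960 + 0.842)² × [p1(1 − p1) + p2(1 − p2)] / (p1 − p2)²

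For A vs B (50% vs 35%): 7.849 × (0.25 + 0.2275) / 0.15² = 166.6, rounded up to 167. The same formula gives 36, 136, 167, 40 and 16 for the other contrasts, all as printed. Only MMR percentages enter, so the two-week outcome plays no part.

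**The case against.** The strongest reply is that this is plainly a slip. The paragraph speaks of outcomes already introduced, the count matches the Objective, and the neighbouring paragraph has the right word. A reader might infer that the sponsor dropped scheduling from this trial, or that it will never be analysed. The documents do not support that: the omission is a fact about the written text, not evidence of intent. The reply does not remove the conflict, because the sentence is the operative instruction and no other text overrides it.

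A reader might also infer that two-week completion puts the personal-contact arms at a disadvantage, since their attempt comes Monday to Friday of the week after the Thursday message. That does not hold, for three reasons.

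- Those arms receive the same automated messages as the message-only arms, plus a later prompt. Measured from the message, all arms have the same 14 days.
- The late prompt would shorten the time left for booking just as it would for attending, so the timing does not measure this error.
- The start of the clock is open. The scheduling outcome is timed from the intervention, while the COVID outcomes are timed from the first intervention.

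The weaker statement survives: attending takes at least as long as booking, and visit supply can delay it. Even that is partial, because the PPC scripts invite families to walk in.

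Finally, the consequence is modest. The outcome is not primary, and power is unaffected. That is accepted.

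**Conclusion.** The inconsistency is real and should be corrected. As written, one of the three Personal Contact outcomes is an undefined variable, and an outcome named in the Objective has no analysis. The six pairwise comparisons planned among the four groups (4 × 3 / 2) would all be made on that variable for this outcome.

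The size is limited. One non-primary outcome in one of the protocol's trials is affected. The MMR analysis, the eight-week completion analysis and the sample size stand. The likely cause is a wording slip. The numerical effect on results cannot be stated from the documents.

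The conclusion assumes only that the outcomes list is the governing definition. The Objective, the MyChart/Televox paragraph and the adolescent SAP all point the same way.

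**What to change.** In the Personal Contact paragraph of the protocol's Analysis section, change the first completed in the outcome list to scheduled, so that the opening reads as it does for the other trials: "scheduled appointment within 2 weeks, completed appointment within 8 weeks". This matches the outcomes list.

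If two-week completion is really wanted, add it to the outcomes list with a definition and a stated clock start, and add the scheduling analysis alongside it.

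The first option costs one word. It probably needs no new data source, though this is inferred. The consent section mentions attendance and MMR records but not booking dates. However, outreach is withheld from parents who book after randomization, so bookings must be tracked. The sponsor should confirm that booking dates are extracted for this trial. If the analysis has already been run, the report should state which variable was used.
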